Title: *ABCA3* gene and RDS in late preterm and term infants

NCT number: NCT04137783

Date of document: March 16, 2021

Neonatal respiratory distress syndrome (RDS) is caused by the deficiency or inactivation of pulmonary surfactant, and is commonly seen in early preterm infants due to their immature lung development. However, some maternal and neonatal characteristics in late preterm and term infants such as maternal diabetes, meconium aspirated pneumonia, neonatal sepsis, and severe intrapartum asphyxia, could also contribute to RDS. Existing evidence has demonstrated that RDS in late preterm and term infants is a somewhat distinct disease entity, with risk factors and clinical profiles that differ from those in early preterm infants ^[1-3]. In a neonatal unit, some late preterm or term infants experience RDS; however, the etiology has not been well defined after a routine workup. This unique RDS entity was referred to as unexplained respiratory distress syndrome (URDS) by numerous previous studies, as well as our study ^[4-7].

Given that a large body of literature has demonstrated the essential role genetic mechanism play in the pathogenesis of most URDS cases, numerous medical facilities have carried out clinical exome sequencing to identify the underlying genetic cause of URDS ^[8-10]. Among all of the genetic factors that contribute to the RDS, the most common is *ABCA3* gene mutation, which involves the assembly of pulmonary surfactant in the lamellar body of pneumocyte II ^[11]. Existing evidence indicated that patients with homozygous or compound heterozygous *ABCA3* gene mutations were commonly in critically ill conditions ^[12]. A single *ABCA3* mutation was also likely to increase the risk and severity of RDS ^[4, 13].

Unfortunately, in a considerable proportion of neonatal URDS patients, genetic testing fails to yield any abnormal findings, making these patients the “true URDS” patients. Currently, whether the *ABCA3*-mutated URDS patients have similar or more challenging clinical profiles to those without any genetic abnormalities continues to confound most neonatologists. An answer to this question would help to guide the management and predict

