the clinical outcomes of neonatal URDS patients. The present study aimed to address this by comparing the clinical characteristics of late preterm and term infants with severe URDS with homozygous or compound heterozygous *ABCA3* mutations, a single *ABCA3* mutation, or no defined genetic abnormalities.

Patient selection

This single-center retrospective cohort study involved infants ≥ 34 weeks' gestation with severe URDS who were admitted to Children's Hospital of Chongqing Medical University between January 2013 and December 2019. In this study, severe RDS was mainly defined according to the consensus of the Pediatric Acute Lung Injury Consensus Conference ^[14], and Montreux definition ^[15]: (1) manifestations and chest radiograph compatible with RDS; (2) on invasive mechanical ventilation with oxygenation index ≥ 16 , which was calculated based on the daily blood gas, or as an alternative measurement, on the subcutaneous oxygen tension ^[16, 17].

Almost all infants with severe RDS had undergone a comprehensive workup, including serial infection markers, chest radiograph, echocardiography, and blood and sputum pathogen testing. For all patients with severe RDS who responded inadequately to interventions and had unremarkable workup findings, trio exome sequencing on samples from patients and their parents were usually recommended. All URDS patients who underwent genetic testing were enrolled in this study. Those whose parents rejected genetic testing, or who had cardiopulmonary malformations, pulmonary hypoplasia, culture-positive sepsis, or known respiratory disease-associated gene mutations (such as *SFTPA1*, *SFTPA2*, *SFTPB*, *SFTPC*, *CHPT1*, *LPCAT1*, *PCYT1B*, *NKX2*, *CFTR*, and *FOXF1*)

were excluded. This study was approved by the Institutional Review Board of Children's Hospital of the Chongqing Medical University (No.2018-158) and was registered on clinicaltrials.gov (NCT04137783).

Exome sequencing and gene mutation detection

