All infants in this study underwent trio exome sequencing after written consent had been obtained from their parents. A gene company (Chigene, Beijing) offered the sequencing as a clinical laboratory service. Sequence analysis of coding exons and flanking introns were performed as previously described^[18,19]. All samples were analyzed to detect frame-shift mutations, nonsense mutations, missense mutations, splicing site mutations, and in-frame indel mutations. Assessment of copy number variation was also performed from exome sequencing data using computational tools. A variant was strictly defined as a mutation if it had been previously described to cause disease with a presentation consistent with these patients, or resulted in an amino acid change or protein structure alteration to disrupt protein function that was predicted by both SIFT and PolyPhen for missense mutations^[20,21], and MaxEntScan and dbSNV for splicing site mutations^[22]. In the case of a novel mutation, phastCons and phyloP were used to determine the evolutionary conservation of the region where the mutation was located^[23]. The American College of Medical Genetics and Genomics/Association for Molecular Pathology (ACMG-AMP) criteria were applied to interpret the mutations^[24]. The subjects in this study were categorized into three groups: homozygous or compound heterozygous *ABCA3* mutations, a single *ABCA3* mutation, and no defined genetic abnormalities.

Clinical profiles data

All relevant clinical data were extracted from a hospital information system.

All antepartum and postpartum data were collected and included: maternal age, parity, and pregnancy-related complications; mode of birth, amniotic fluid condition, and history of asphyxia and resuscitation; postnatal age of respiratory symptom onset, modalities of respiratory support, and the daily record of blood gas and subcutaneous oxygen tension; laboratory data including complete blood count, C-reactive protein, procalcitonin, blood and sputum culture, respiratory viral detection test, and genetic testing; radiographic examination including chest X-ray and echocardiogram; medications taken during the hospital stay.

Radiological scoring

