All chest X-rays were reviewed on a hospital information system by one radiologist. The most severe images were scored according to the Fleischner Society criteria^[25]. The chest X-ray was rated in three sections on both sides of the lung: apex to the carina, carina to the lower pulmonary vein, and lower pulmonary vein to the diaphragm. The incidence of radiological features, including ground-glass opacity, reticular pattern, air bronchogram, atelectasis, and air leak, were evaluated for each lung section. Each finding was scored as 0 = none, 1 = discrete, 2 = diffuse, or 3 = strong at each section. An overall cumulative score was calculated by adding the individual section scores together, with a maximum score of 18 for each patient.

Statistical Analysis

Analysis of variance (ANOVA) and the Chi-square or Fisher's exact tests were used to compare clinical characteristics and radiographic scores between different groups of patients. Tests for the differences in the age of symptom onset and the age of development of severe RDS between the groups were carried out using the log-rank test. A two-tailed *p*-value of

<0.05 was considered statistically significant.

References

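### The genotype comparisons are all unadjusted; a supportive analysis accounting for gestational age would show whether any ABCA3 difference holds at the same gestation

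*Combined protocol and SAP*

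**What the plan says.** The document's aim is "comparing the clinical characteristics of late preterm and term infants with severe URDS" across three genotype groups: homozygous or compound heterozygous (biallelic) *ABCA3* mutations, a single *ABCA3* mutation, and no defined genetic abnormality. Under Patient selection, the design is a single-centre retrospective cohort of infants of at least 34 weeks, and "All URDS patients who underwent genetic testing were enrolled in this study".

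Under Statistical Analysis, ANOVA and chi-square or Fisher's exact tests "were used to compare clinical characteristics and radiographic scores between different groups of patients". Differences in age at symptom onset and "age of development of severe RDS between the groups were carried out using the log-rank test", with two-tailed p<0.05. No section names a covariate, stratification factor, matching, regression model or late-preterm/term subgroup.

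Under Clinical profiles data, "All relevant clinical data were extracted from a hospital information system". The itemised list begins "All antepartum and postpartum data were collected and included: maternal age, parity, and pregnancy-related complications" and does not name gestational age. It is worded as inclusive, so it may not be exhaustive.

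The opening background asks whether mutated "patients have similar or more challenging clinical profiles to those without any genetic abnormalities" and adds: "An answer to this question would help to guide the management and predict" clinical outcomes.

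**The concern.** Gestation enters the plan only as a lower limit of 34 weeks. That sets a floor but does not balance the groups.

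Genotype is fixed before gestation, so gestation is not a common cause of genotype and outcome. The route to an imbalance is selection. If a mutation and lower gestation are separate ways of reaching severe RDS, they can be associated among the selected cases even when they are unrelated at birth. Carriers would then tend to be more mature than infants without a defined abnormality.

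If severity or timing also varies with gestation above 34 weeks, the unadjusted contrast mixes the two. It could show a difference that disappears at equal gestation. It could also hide one: more mature biallelic infants could look no worse than the comparison group although they are worse than infants of the same gestation. The second error matters most for a reader who uses the result to guide management or predict outcome.

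**Working it through.** The plan gives no sample size, group sizes, gestational-age distribution or severity gradient, so there is no figure to reproduce. Every number below is illustrative.

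**Assumed inputs.** Groups of 30/15/10 (none/single/biallelic). Genotype independent of gestation in the source population. Risk of severe RDS without mutation 1% at 34 weeks, odds falling 20–40% per week (OR 0.8 to 0.6). Severity falling 0.1–0.3 SD per week. No genotype effect on severity at a given gestation.

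**Step 1: can selection produce a gap?** Without a mutation, the odds at week w are (0.01/0.99) × OR^(w−34), and risk p0 = odds/(1+odds). In model (a), mutation as an added independent cause, risk = 1 − (1 − p0)(1 − c), with c = 0.5 for biallelic and 0.01 for single. Take source gestation uniform over 34–41 weeks and OR 0.6:

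- None: p0 falls from 0.0100 at 34 weeks to 0.00028 at 41. Mean gestation = Σ(w·p0)/Σp0 = 0.8726/0.02467 = 35.4 weeks.
- Biallelic: risk is 0.5 + 0.5·p0, so 0.505 at 34 weeks and 0.500 at 41, almost flat. Mean 37.5 weeks.
- Gap: 37.5 − 35.4 = 2.1 weeks.

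With OR 0.8 the none mean is 1.5197/0.04176 = 36.4 and the gap 1.1 weeks.

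In model (b) the mutation multiplies the odds (50 for biallelic, 3 for single), and the gap is only about 0.2 weeks.

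**Step 2: how often would ANOVA reject with no genotype effect at a given gestation?**

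| Model | Source gestation | Gap, weeks | ANOVA | Adjusted for gestation |
|---|---|---|---|---|
| (a) | Uniform, 34–41 weeks | 1.1–2.1 | 5–33% | about 4–5% |
| (a) | Term-weighted* | 0.5–1.3 | 5–16% | about 4–5% |
| (b) | Uniform, 34–41 weeks | about 0.2 | 4.5–5.9% | 4.3–5.8% |

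*Weeks 34 to 41: 1, 1.5, 3, 8, 20, 35, 22, 9.5%.

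**Step 3: log-rank.** Under (a) with uniform gestation and an onset hazard falling 10–30% per week, the unstratified test rejects in 7–39% of samples, against 6–7% when stratified at 34–35, 36–37 and ≥38 weeks. With no gestation effect at all it already rejects in about 7%, so only the excess over 7% reflects gestation. The term-weighted source was not run for the log-rank test.

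A separate simulation set the late-preterm shares directly (10/30/70% for biallelic/single/none, 15/15/30 infants). With gestation hazard ratios of 1.5, 2 and 3, the unstratified test rejected in 9.8%, 19.8% and 31.4%, against 6.1–6.7% when stratified by late preterm/term. With equal shares both tests stayed near 7%. Late preterm versus term was the only gestation effect there, so it does not show how well two strata handle a gradient within each stratum.

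**Step 4: masking.** The unadjusted difference is roughly the true difference minus gradient × gap. For a true biallelic disadvantage of 0.8 SD under (a):

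- Uniform: 0.8 − 0.3 × 2.1 = 0.17 SD to 0.8 − 0.1 × 1.1 = 0.69 SD (simulated 0.15–0.68). Adjusted: 0.79–0.81 SD if slopes are equal.
- Term-weighted: 0.8 − 0.3 × 1.3 = 0.41 SD to 0.8 − 0.1 × 0.5 = 0.75 SD.

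**Step 5: would the characteristics table reveal it?** Under (a) with uniform gestation, an ANOVA of gestation itself gives p<0.05 in 25–86% of samples. When it does not, the mean gap is still 0.8–1.2 weeks, although the outcome ANOVA then rejects in only 4.5–8%.

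**Step 6: limits of adjustment.** If biallelic severity does not vary with gestation and its mean equals that of the none group, the unadjusted difference is 0.0 SD, but a common-slope model reports 0.09–0.50 SD under (a). A slope-by-genotype test detects this in only 7–35% of samples.

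**The case against.** The strongest reply is that the aim is descriptive. It is to compare clinical characteristics between genotype groups, not to estimate a gestation-independent effect of *ABCA3*. Under model (a) the groups really do differ in mean severity, so a rejection correctly detects a descriptive difference. It is false only for a gestation-conditional contrast, which the plan does not state as its objective. This stands, and it is why the planned tests should stay. It does not settle the matter, because the background asks whether mutated infants are in a worse position and offers the answer for management and prognosis.

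The second reply is that nothing in the documents supports an imbalance or a gradient. The background ties lung immaturity to early preterm infants, whom the study excludes, and treats RDS in later gestations as a somewhat distinct entity. This also stands. The size depends on the source distribution and on how the mutation acts, and the 33% figure is the extreme corner of one set of assumptions.

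Third, gestation must be known to apply the 34-week limit and could be compared as a clinical characteristic. That would show a gap, but not what genotype difference remains after it.

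Fourth, with about ten biallelic infants a common-slope model can itself mislead, as step 6 shows. This stands and shortens the remedy.

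A reader might infer that the groups are in fact imbalanced, that the planned tests are invalid, or that gestational age was not collected. The documents support none of these.

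**Conclusion.** The point holds as a cheap improvement, not as a flaw that undermines the study. No planned analysis accounts for gestation, so the plan cannot say whether *ABCA3* infants are similar or worse at the same gestation. Whether this changes any result is unknown.

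With no genotype effect at a given gestation, rejection by ANOVA ranges from baseline to about 16% (term-weighted) or 33% (uniform) if the mutation is an added independent cause, and stays near baseline if it multiplies the odds. These ranges rest on assumed group sizes, risks and gradients. They should not be read as the study's error rate.

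**What to change.** - Keep the unadjusted tests as the descriptive comparison.
- Name gestational age in weeks as an extracted variable and show its distribution by genotype group, not only a p-value.
- Beside the radiographic-score comparison and the two age-at-event comparisons, report one supportive analysis with gestation as the only covariate: a linear model for the score, and Cox regression or a late-preterm/term-stratified log-rank test for the times. Label it post hoc if results have already been seen.
- Plot each outcome against gestation by group. Where overlap is poor or slopes differ, state that gestation cannot be separated from genotype and do not rely on the common-slope estimate.
- State that all comparisons are conditional on severe, genetically tested unexplained RDS. Adjustment for gestation does not remove selection through unmeasured causes or refused testing.

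**Cost.** One variable already needed for eligibility, and one extra result beside each of three comparisons. Some precision is lost in small groups. With OR 0.6 and no gestation effect on the outcome, the simulated standard error of the biallelic-versus-none difference rose from 0.359 to 0.395 (10%) at 30/15/10 and from 0.476 to 0.535 (12%) at 15/8/6. In many scenarios with a steeper gradient it fell. The remaining risk is misfit if slopes differ, hence the plots.

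### The two log-rank comparisons of age name no small-sample version; if genotype groups are small, the usual chi-square p-value can exceed its 5% level modestly, and a permutation p-value would hold it

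*Combined protocol and SAP*

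**What the plan says.** All of this is in the combined protocol and SAP.

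- **Outcomes and test (Statistical Analysis).** Two outcomes are treated as times, namely age at first symptoms and age when RDS became severe. Their comparisons "between the groups were carried out using the log-rank test". Nothing says whether the p-value is asymptotic or exact, or whether the test is a three-group or a pairwise one.
- **Threshold (Statistical Analysis).** The level is two-sided and applies to every test: "<0.05 was considered statistically significant".
- **Other comparisons (Statistical Analysis).** Besides ANOVA, "Chi-square or Fisher's exact tests were used to compare clinical characteristics". An exact method is thus named for categorical data.
- **Groups (Exome sequencing and gene mutation detection).** "The subjects in this study were categorized into three groups": biallelic *ABCA3* mutations, a single *ABCA3* mutation, or no defined abnormality.
- **Entry (Patient selection).** Severe RDS requires being "on invasive mechanical ventilation with oxygenation index" of at least 16. "All URDS patients who underwent genetic testing were enrolled in this study", subject to the listed exclusions.

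The documents give no total sample size, group sizes or power calculation.

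**The concern.** An infant must have severe RDS to be in the cohort, so both ages are known for everyone and the log-rank test is applied to complete data. Its usual p-value comes from a chi-square approximation that needs reasonably large groups. This is a single-centre cohort of infants at 34 weeks or more with severe unexplained RDS who had trio sequencing, and it is then split three ways by genotype. Small groups are a reasonable expectation, though not a stated fact.

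If the approximation is poor, a printed p just under 0.05 overstates the evidence. These are the plan's only two time comparisons. The plan names no primary endpoint, so each p-value is likely to be read against 0.05 on its own.

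**Working it through.** **Inputs.** From the documents: three groups, two outcomes, threshold 0.05, and no censoring (inferred from the entry criterion). Assumed: the chi-square reference, as the usual software default, and the group sizes, as a range. Time resolution is only hinted at. Patient selection bases the oxygenation index on daily blood gas, so age at severe RDS is plausibly known only to the day. The resolution of onset age is not stated.

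**Statistic.** At each distinct age with d events among n infants at risk, of whom n_g are in group g, the expected count is E_g = d × n_g / n. Summing O − E over ages and using the hypergeometric covariance V gives X² = (O − E)′ V⁻ (O − E). This is referred to chi-square on 2 df, with 5% cut-off 5.991. A simpler form sums (O − E)²/E over groups.

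**The plan's own figure.** The only stated figure is the 5% threshold. It cannot be reproduced as an attained level, because neither the group sizes nor the reference distribution is given.

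**Level under the null, by simulation.** There were 100,000 data sets per design for untied ages (Monte Carlo standard error about 0.08 points) and 50,000 for exponential ages rounded up to whole days with mean 3 days. The code agreed with a standard log-rank routine on tied test data.

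| Assumed sizes | Untied, chi-square | Whole days, mean 3 | Untied, (O − E)²/E form |
|---|---|---|---|
| 3, 5, 20 | 10.4% | 7.3% | 8.1% |
| 5, 5, 20 | 9.1% | 6.8% | 6.9% |
| 5, 10, 30 | 8.2% | 6.8% | 6.5% |
| 8, 12, 40 | 7.4% | 6.2% | 5.9% |
| 10, 10, 10 | 7.5% | 6.6% | 5.2% |
| 15, 15, 15 | 6.8% | 6.1% | 5.1% |
| 15, 20, 40 | 6.4% | 6.0% | 5.2% |
| 20, 20, 40 | 6.1% | 5.8% | 5.0% |
| 30, 30, 60 | 5.8% | 5.5% | 5.0% |
| 50, 50, 100 | 5.4% | 5.4% | 4.8% |

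Equal groups of 10 or 15 are inflated too, so small size is the main driver rather than imbalance.

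**Heavier ties.** Smaller runs with ages rounded up to days gave about 3.5-5.6% when the mean age was 1 day and about 5.0-6.2% when it was 2 days.

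**Pairwise tests, untied.** 9.0% at 3 v 20, 7.4% at 5 v 20, 6.2% at 10 v 30 and 5.6% at 20 v 40.

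**Permutation p-value.** With no censoring and equal age distributions under the null, group labels are exchangeable given the pooled ages. For B random relabellings, p = (1 + number with X²* ≥ X²) / (B + 1), and p ≤ 0.05 then occurs at most 5% of the time. Simulated levels were 4.9-5.2% in six untied designs. With whole-day ages they were 3.8%, 5.3% and 5.8%, from 1,200, 1,200 and 400 data sets. The standard errors at 5% are √(0.05 × 0.95 / 1,200) = 0.6 points and √(0.05 × 0.95 / 400) = 1.1 points, so these fit a level of about 5% or slightly below.

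**Rejection rates under real differences, untied.** Hazard ratios are in the order biallelic : single : none.

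| Sizes | Hazard ratios | Chi-square | Permutation |
|---|---|---|---|
| 5, 5, 20 | 2:1:1 | 28.3% | 19.1% |
| 5, 10, 30 | 2:1:1 | 30.1% | 22.5% |
| 8, 12, 40 | 2:1:1 | 39.6% | 32.8% |
| 15, 20, 40 | 2:1:1 | 57.6% | 53.4% |
| 20, 20, 40 | 2:1:1 | 66.4% | 62.7% |
| 5, 5, 20 | 0.33:0.67:1 | 41.4% | 26.8% |

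**The case against.** **The inflation is conditional.** The sizes are unknown, and the chi-square reference is inferred because the plan says only log-rank. The simpler (O − E)²/E form is close to nominal once the smallest group has about 10 to 15 infants. Daily dating makes ties plausible for at least one of the two ages, and ties shrink the inflation or remove it. All of this stands, and it limits how large the effect can be said to be.

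**The practical weight is low.** This is a retrospective, descriptive comparison with no power claim and many unadjusted tests. A shift of one to four points in the level of two of them matters only for p-values near 0.05. This also stands, and it sets the priority.

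**What it does not answer.** The plan leaves the attained level of these two tests undefined. A permutation p-value settles it without anyone needing to know the sizes, the ties or the software default. With large groups it should differ little from the chi-square p-value.

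**A stronger reading about the test itself.** A reader might infer that the log-rank test is the wrong choice because nothing is censored. The documents do not support that: the test is legitimate on complete data, and only the reference distribution is in question. A switch to Kruskal-Wallis is not needed and can lose power. In one simulation at (8, 12, 40) with exponential ages, power at exact size was 74% for log-rank and 59% for Kruskal-Wallis. With lognormal and log-logistic ages the two were about equal.

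**Conclusion.** The concern holds in a conditional form. If the smallest group has about 5 to 20 infants and the chi-square reference is used, the true level is about 6-9% with untied ages and about 5.5-7% with whole-day ages averaging about 3 days. It is near 5% or below if ages cluster in the first day or two, and about 6% or less once every group has about 30 infants. The assumptions are the group sizes, the chi-square default and the spread of ages. Absence of censoring is a fair inference from the entry criterion.

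A reader might go further and conclude that this study's tests do run at 6-9%, that a result just under 0.05 is a false positive, or that one corrected cut-off should replace 5.991. None of these follows. The sizes and time resolution are not in the documents, and the right cut-off changes with both. Priority: minor.

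**What to change.** Add one sentence to the Statistical Analysis section: for age at symptom onset and age at severe RDS, the log-rank statistic is kept and its p-value is taken from the permutation distribution of group labels, for example with 10,000 permutations. State also whether the test is three-group or pairwise, and the unit in which each age is recorded.

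The cost is a few lines of code, with no extra infants or data. It is not free in another sense: some p-values just under 0.05 will cross the threshold, and nominal rejection rates under real differences fall, for example from about 40% to 33% at (8, 12, 40) with hazard ratios 2:1:1. Part of that fall is only the inflated level being removed.
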